### **3.8. Subgroup Analysis**

Subgroup analyses may be conducted to investigate the similarities across different age brackets, Japanese/non-Japanese patients, sex, race, ethnicity, and regions. The following designations may apply:

#### **Age Brackets**

- Patients  $< 12$  years old (i.e., 4-11 years old)
- Patients  $\geq 12$  and  $< 18$  years old (i.e., 12-17 years old)
- Patients  $\geq 18$  years old

#### **Japanese/Non-Japanese Status**

- Japanese
- Non-Japanese

#### **Sex**

- Male
- Female

#### **Race**

- White
- Black
- Other (other races will be included if number of patients is greater than or equal to 10)

#### **Ethnicity**

- Hispanic or Latino
- Not Hispanic or Latino

#### **Region**

- North America (Canada, United states)
- Europe (Germany, Netherlands, United Kingdom)
- Japan

Analysis of the primary efficacy, and appropriate secondary and exploratory efficacy endpoints may be repeated for these subgroups should sufficient numbers of patients exist.

For subgroup analyses where the subgroup variable is a term in the model, these terms will be excluded from the model for that subgroup analysis and individual estimates will be generated for each grouping.

Any such analyses or descriptive summaries to be generated will be outlined in the sections below.

### **3.9. Withdrawals, Dropouts, Loss to Follow-up**

Patients who are withdrawn or discontinued from the study will not be replaced.

### **3.10. Missing, Unused, and Spurious Data**

Missing data will be handled for height and body weight and, by extension, their derivatives (BMI, BMI Z-Score, BMI P95), daily hunger scores, and adverse event dates.

Imputation of other missing questionnaire data will be applied for the derivation of summary scores, dependent on the questionnaire and imputation rules of the questionnaire.

Unless otherwise specified, all other study data will be summarized as reported (missing data will not be imputed).

#### **3.10.1. Height**

Given that height will be measured only at screening for patients 21 years of age or older, for visits where weight is collected but height is not, BMI will be calculated using the last available height measurement prior to weight collection (LOCF). The same approach is planned to be used for patients less than 21 years old as this will provide a conservative estimate of the BMI (as height is expected only to increase over the course of the study yet will be held constant in this approach, resulting in higher/more conservative BMI).

#### **3.10.2. Weight**

For analyses of weight and its derivatives (BMI, BMI Z-Score, BMI P95), including the primary and key secondary efficacy analyses, multiple imputation (MI) will be used to model missing weight measurements at the primary timepoint (after 52 weeks of therapeutic treatment). BMI, BMI Z-score, and BMI P95 will then be derived based upon the imputed weight and available height records.

Weight will be imputed using a retrieved dropout (RD) approach utilizing the following steps:

- If non-monotone missingness is observed in the full set of observations (inclusive of on-treatment completers), Markov Chain Monte Carlo will first be utilized on the full set of observations according to treatment arm to impute intermediate values and to generate a monotone missingness pattern.

- From there, or if a monotone pattern is naturally observed in the data, 2 subsets will be generated:
  - Subset 1: patients classified as off-treatment at primary timepoint (RDs or non-RDs)
  - Subset 2: on-treatment completers
- Monotone regression MI will then be applied to Subset 1 according to treatment arm, regressing on baseline weight, Visit 2 weight, Visit 4 weight, Visit 7 weight, Visit 9 weight, Visit 11 weight, and primary timepoint weight. This will result in 100 complete Subset 1 datasets (either as result of impute = 100 MCMC and impute = 1 Monotone, or, impute = 100 Monotone, missingness structure dependent).
- The complete Subset 1 data will be combined with Subset 2 data to give a wholly complete dataset, representative of all patients (Subset 1 and Subset 2)

Should there be insufficient RD to provide a reliable multiple imputation model, a wash-out imputation method will be utilized.

For wash-out imputation, placebo patients will first be imputed assuming missing-at-random (MAR) regressing on baseline weight, Visit 2 weight, Visit 4 weight, Visit 7 weight, Visit 9 weight, Visit 11 weight, and primary timepoint weight. This accounts for planned on-site visits as well as a combined primary timepoint as outlined in [Table 3-1](#) below.

If non-monotone missingness is observed, MCMC MI will be utilized according to treatment arm to impute intermediate values and to generate a monotone missingness pattern. From there, or if a monotone pattern is naturally observed in the data, MI utilizing monotone regression will be executed.

Once the placebo patients have been imputed under MAR as directed above, the observed placebo patients will be combined with the setmelanotide patients needing imputation of the primary timepoint. The setmelanotide patients will then be imputed assuming missing-not-at-random (MNAR) using placebo-based imputation (jump to reference method) regressing only on baseline value and primary timepoint value.

Under either imputation method, should there be a patient death while on study, the patient will be considered as a treatment failure and the effective change and percent change from baseline will be set to 0 once the imputation is complete.

Regardless of if RD MI or wash-out MI is utilized, one hundred imputed datasets will be generated via SAS PROC MI. Each of the imputed datasets will then be analyzed according to the relevant statistical test outlined in the sections below. Resulting estimates will be combined using Rubin's rule (SAS PROC MIANALYZE) to produce inferential results.

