### 3. GENERAL STATISTICAL METHODS

#### 3.1. Sample Size Justification

The sample size is mainly driven by the primary efficacy hypothesis with the safety database taken into consideration. With the planned sample size of ~120 patients (~80 patients in setmelanotide group vs ~40 patients in placebo group), the trial provides ~99.5% power to detect a treatment difference (treatment - placebo) of -10% in percent change of BMI from baseline after approximately 52 weeks on a therapeutic regimen of setmelanotide at 2-sided alpha of 0.05, assuming a common standard deviation of 10% (estimated from trial RM-493-030), a dropout rate of 20%, and 2:1 randomization.

It is planned to enroll ~12 patients from Japan within the ~120 patients. Using the Method 1 described in PMDA guidance, simulation studies (nsim = 100000 runs) confirmed that the sample size of 12 Japanese patients will provide 80.1% probability that  $D_{\text{Japan}}/D_{\text{all}} > 0.5$  (D: Difference between study drug and placebo for the primary endpoint).

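### Imputing weight in kilograms across ages 4 to adult with no age term makes imputed BMI changes in young children far too variable, costs precision, and rests on a first-choice model that placebo retention will probably not support

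*SAP*

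**What the plan says.** SAP 3.10.2 makes weight the imputed variable. After any MCMC step that produces a monotone pattern, the off-treatment patients of each arm are imputed as follows: "Monotone regression MI will then be applied to Subset 1 according to treatment arm, regressing on baseline weight, Visit 2 weight, Visit 4 weight", then Visits 7, 9 and 11 and the primary timepoint. Then "BMI, BMI Z-score, and BMI P95 will then be derived based upon the imputed weight and available height records".

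If retrieved dropouts (RDs; off-treatment patients with the endpoint observed) are too few, the method changes: "Should there be insufficient RD to provide a reliable multiple imputation model, a wash-out imputation method will be utilized". Under wash-out, placebo patients are imputed as missing at random from the same visit weights. Setmelanotide patients are imputed from placebo, "regressing only on baseline value and primary timepoint value". No minimum RD number is given. SAP 3.10.3 mentions only whether the RD approach converges, and lets weight and hunger use different methods.

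No imputation model lists age, sex, height or stratum. The primary ANCOVA in SAP 4.3.2 adjusts for three age groups, and the responder tests in 4.3.5 are stratified by age group.

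SAP 3.10.1 carries the last height forward where weight is collected without height, including under 21 years, and argues that "this will provide a conservative estimate of the BMI" because height can only rise.

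**The concern.** The endpoint is a percent change, but the imputation noise is in kilograms. A linear regression with one residual variance gives a child the same kilogram scatter as an adult of more than twice the weight, so the child's percent change is much too noisy. Growth adds a second problem: imputed weight includes later growth, while the height used to compute BMI may not. A third is whether the first-choice regression can be fitted at all with the expected number of placebo patients off treatment.

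These imputed values feed the primary endpoint. They also feed both BMI-based key secondary endpoints (SAP 4.3.5), the paediatric Z-score and percent-of-95th-percentile analyses (4.3.6.6, 4.3.6.7), and the BMI threshold analysis (4.3.6.8).

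**Working it through.** **Inputs from the documents.** 80 vs 40 patients, 20% dropout, SD 10%, difference -10 points, 2-sided alpha 0.05 (SAP 3.1); age 4 years and over (Protocol 4.1); the models quoted above. **Assumed, because the documents give no figures:** age mix (under-12 share 10-35%); mean baseline BMI 28, 35 and 40 kg/m² and height 130, 160 and 168 cm for under 12, 12-17 and adult; placebo mean change +2%; growth 0-6 cm/yr under 12.

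**1. The plan's own figure.** The SAP states that "the trial provides ~99.5% power to detect a treatment difference (treatment - placebo) of -10% in percent change of BMI". After 20% dropout: 64 vs 32, SE = 10 × √(1/64 + 1/32) = 2.165, and 10/2.165 = 4.62. The noncentral t with 94 df gives 99.55%; the normal approximation gives 99.61%. The figure reproduces.

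**2. Dispersion.** The assumed mean weights are 28 × 1.30² = 47 kg, 35 × 1.60² = 90 kg and 40 × 1.68² = 113 kg. With a 20-35% under-12 share, the fitted wash-out residual SD was about 9.1-10.3 kg. As a share of body weight that is 19-22% for the child, 10-11% for the adolescent and 8-9% for the adult. The simulated SDs of imputed percent BMI change agree (truth 10):

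| Model | <12 | 12-17 | Adult |
|---|---|---|---|
| Wash-out (baseline weight only) | 20-24 | 10.7-12.6 | 8.5-10.2 |
| Multi-visit regression | 14-18 | 10.4-11.1 | 9.6-10.0 |

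Further wash-out runs with other assumed mixes and sizes gave 22-28 under 12 and 11-13 at ages 12-17.

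**3. Growth.** Without growth the under-12 imputed mean is 2.0-2.3, against a truth of 2. At 3-6 cm/yr it is 3.4-6.7 (wash-out) and 3.0-6.5 (multi-visit), a bias of about +1 to +5 points. Other runs at 5 cm/yr gave about +7 to +8. At ages 12-17 the bias is about 0 to +1.4. As an upper illustration, holding height at 130 cm while the child reaches 135 cm overstates BMI by (135/130)² - 1 = 7.8%.

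**4. Responders.** With placebo-like outcomes, the wash-out share of under-12s with at least a 5% BMI reduction is 0.28-0.38, against a true 0.24.

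**5. Primary comparison.** 600 simulated trials per scenario, 25 imputations, 20% missing in each arm, wash-out. Placebo dropouts were seen through Visit 7, and the ANCOVA was simplified (equal variance, age group only). The comparator imputes percent BMI change with an adult/child term.

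| <12 share; growth in <12; effect | Estimate kg / % | Mean SE kg / % | Rejection kg / % |
|---|---|---|---|
| 20%; 0 cm/yr; -10 | -7.98 / -7.98 | 2.55 / 2.28 | 0.948 / 0.978 |
| 20%; 6 cm/yr; -10 | -8.00 / -8.00 | 2.59 / 2.28 | 0.938 / 0.975 |
| 35%; 6 cm/yr; -10 | -8.07 / -8.09 | 2.66 / 2.28 | 0.942 / 0.983 |
| 20%; 6 cm/yr; 0 | 0.03 / 0.03 | 2.46 / 2.17 | 0.007 / 0.015 |

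The fall from -10 to about -8 is what wash-out does by design (0.8 × -10). SE ratios for the -10 rows: 2.55/2.28 = 1.12 to 2.66/2.28 = 1.17.

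**6. Retrieved-dropout model.** Six weights plus an intercept make 7 coefficients, so residual df = RDs - 7. Planned placebo dropouts: 0.20 × 40 = 8. If all 8 have the endpoint, none of them needs imputing; if one lacks it, at most 7 RDs remain and df ≤ 0. Taking 20% off treatment as a probability, with 25, 50 or 75% retrieved, expected placebo RDs are 2, 4 and 6. P(at least 8), from binomial(40; 0.05, 0.10, 0.15), is 0.001, 0.04 and 0.24. At 30% off treatment and 60% retrieved it is 0.43. For setmelanotide at 50% retrieved, binomial(80; 0.10) gives 0.55. With exactly 8 RDs (1 df), the drawn residual SD exceeds 8 times its estimate with probability P(chi-square with 1 df < 1/64) = 0.10.

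**The case against.** The strongest reply is that the primary test is not compromised. That stands: with equal dropout the estimate is the same under both methods and rejection under no effect is below nominal. A reader might infer that the imputation biases the trial toward setmelanotide. The documents do not support that. An inflated BMI in a wash-out setmelanotide child works against the drug, and a net gain would need growing placebo children to be missing disproportionately, which nothing in the plan implies.

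A reader might also infer that the primary analysis cannot be run. It can: SAP 3.10.2, SAP 4.3.1 and Protocol 7.4 all foresee too few RDs and pre-specify wash-out. The count of 8 also takes the 20% as all patients off treatment. If it means 8 missing endpoints, 8 further RDs would be needed, or 16 of 40 off treatment.

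Other parts of the reply also stand. Applying the carried-forward height to an imputed weight is an inference from the wording on available heights. Height under 21 is scheduled throughout, so only growth after the last measurement is lost. Few patients are involved: with 20% missing and an assumed 25% under 12, 120 × 0.20 × 0.25 = 6 children, about 4 active and 2 placebo. Tipping-point, as-observed and LOCF analyses are planned. None of this justifies a kilogram-scale model for a percent endpoint, or leaves a stated threshold for the fallback.

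**Conclusion.** The point holds as a should-fix. The over-dispersion under 12 is structural: it follows from one kilogram variance across unequal body sizes. Its size (SD about 20-28% in wash-out, 14-18% in the multi-visit regression, against 10%) depends on the assumed age mix and body sizes. Ages 12-17 are little affected.

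The upward bias is conditional on growth after the last height: about +1 to +8 points at 3-6 cm/yr, none without growth. The conservative label therefore does not hold for imputed placebo children, where a higher BMI enlarges the apparent treatment difference.

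For the primary endpoint the cost is precision: an SE about 12-17% larger and rejection of 0.94-0.95 instead of 0.975-0.98, under equal dropout. Responder and paediatric outputs are distorted. The RD model is unlikely to be usable in placebo at the planned dropout, so wash-out is the likely primary method, reached through a trigger that has no number.

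**What to change.** Impute log BMI or percent BMI change at the primary timepoint, with age group and baseline BMI in every imputation model, and derive Z-score and percent of the 95th percentile from the imputed BMI.

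Keep the RD model within arm, as Protocol 7.4 and SAP 4.3.1 require, but reduce it to baseline BMI plus an adult/child term, without intermediate visits. It then has 3 coefficients: 7 RDs leave 4 df, and 4 RDs leave 1. State the minimum RD count per arm that this model needs. It must be reachable with about 8 placebo dropouts; a threshold of 10 per arm, for example, would rule the method out in advance. If either arm falls short, use wash-out for both arms. Decide before outcomes are unblinded, with the count made by someone outside the study team who sees arm and retention status only.

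Delete the conservative statement in SAP 3.10.1, or limit it to cases where it is true.

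Cost: SAP wording and re-programming, with no new data. Imputed weight for the weight endpoints must be back-calculated from BMI and height, which brings the height problem with it, or imputed separately on a log or percent scale. Protocol 7.4 does not fix the imputation scale, but Protocol Section 7 requires an amendment for major changes to the primary analysis, so the sponsor should record whether this is one.

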### Treatment Period

To enter the Treatment Period on Day 1 and prior to randomization, the trial center must confirm that patients have completed the Screening assessments, including the e-diary at least 4 of the 7 days prior to the baseline visit. If the e-diary is not appropriately completed before the baseline visit, patients may be asked to complete the e-diary collection and re-schedule randomization and the baseline visit if the remaining visit window allows. Throughout the trial, patients (or caregivers) will need to complete the e-diary entries.

The Treatment Period is intended to last until each patient has been dosed for 52 weeks on a therapeutic regimen (56 weeks to 60 weeks). Trial drug administration details are provided in [Section 5.5.3](#) and

**Table 6.** During the Treatment Period, patients will attend in-clinic visits and may attend at home tele-health visits at Weeks 8, 16, 20, 28, 36, 44, 52 at the discretion of the investigator. Patients and caregivers will complete the assessments listed in the SoA (Table 1). Detailed assessment information is provided in Section 6.

CCI

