- † The Week 8, 16, 20, 28, 36, 44, and 52 visits may be scheduled in-clinic or as at home telehealth visits at the discretion of the Investigator. If these visits are conducted as telehealth visits, the following assessments are not required to be collected: height, weight, waist circumference (cm), vital signs. For patients on hormone replacement therapy, one or more of these visits may be required in-person. See [Section 6.8.6](#).
- †† The EOT visit occurs after 52 weeks on a therapeutic regimen. CCI [REDACTED]
-  All patients will initiate setmelanotide at 0.5 mg once daily (QD). The first dose will be administered in clinic. Dose titration will be made per [Section 5.5.3](#).
-  The SFV visit will occur 14 days after the last dose of trial treatment (ETT) for patients who prematurely discontinue. The SFV is not required for patients who complete the EOT Visit and enroll in the optional LTE. For LTE eligibility, see [Section 5.1.3](#).
-  Prior to the initiation of any trial procedures and assessments, signed informed consent and/or assent (as applicable) are required per protocol. A separate informed consent and/or assent (as applicable) will be required CCI [REDACTED]. Additional considerations for reducing pain in distress in patients younger than 18 years of age are included in [Appendix 2](#).
-  CCI [REDACTED]
-  A complete physical examination will be conducted at Screening and at the EOT Visit (or at the ETT Visit, as applicable). At other time points, an abbreviated examination will be performed. The abbreviated examination should focus on heart, lungs, skin, and any areas of previous abnormal findings, noting any changes from baseline. In addition, Tanner Staging for assessment of pubertal development will be conducted for those patients who have yet to reach Tanner Stage V. Whenever possible, the same trained health care professional will conduct the exam and Tanner Staging.

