#### 3.2. General Methods

All data listings that contain an evaluation date will contain a relative study day (Rel Day). Pre-treatment and on-treatment study days are numbered relative to the date of randomization which is designated as Day 1. The preceding day is Day -1, the day before that is Day -2, etc. The last day of study medication is designated with an "L" (e.g., Day 14L). Post-treatment study days are numbered relative to the last dose and are designated as Day 1P, Day 2P, etc.

All output will be incorporated into Microsoft Word or Excel files, or Adobe Acrobat PDF files, sorted and labeled according to the International Conference on Harmonisation (ICH) recommendations, and formatted to the appropriate page size(s).

Tabulations will be produced for appropriate demographic, baseline, efficacy, pharmacokinetic, and safety parameters. For categorical variables, summary tabulations of the number and percentage of patients within each category (with a category for missing data) of the parameter will be presented. For continuous variables, the number of patients, mean, median, standard deviation (SD), minimum, and maximum values will be presented.

Unless stated otherwise, all relevant statistical tests will be conducted at the 2-sided, 0.05 level of significance.

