**3.11.1. Therapeutic Dose Start Date and Primary Timepoint**

Efficacy data will be summarized formally at the primary timepoint, after 52 weeks on therapeutic dose.

Setmelanotide or placebo equivalent will be administered at starting doses in all patients and subsequently up-titrated towards the target therapeutic dose, CCI dependent. CCI

[REDACTED]

[REDACTED]

[REDACTED]

[REDACTED]

CCI  
.

To identify the primary timepoint, the following steps will be utilized:

- Calculate the number of days from therapeutic dose start date for all on-site visits excluding bridging visits
- The non-missing, on-site visit occurring closest to day 365 within a window of 305 to 425 days from therapeutic dose start date will be selected
- If multiple results are equidistant from Day 365 (from the therapeutic dose start date), the latest of these equidistant results is selected
- If no results have been reported within days 305 to 425 from therapeutic dose start date, then the primary timepoint is considered missing

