3.11.2. Efficacy Windowing for Patients

As noted in Section 3.10.2, RD MI and washout MI methodologies will impute based on results from baseline, Visit 2, Visit 4, Visit 7, Visit 9, Visit 11, and the primary timepoint. To ensure that captured data is used to the greatest extent possible, expanded windows as compared to the SOA will be considered. Note that visit windowing and use of on-site additional, unscheduled, or early termination visits will only occur if the specific visit as recorded and tabulated per the CRF is missing. That is, for on-site Visits 2, 4, 7, 9, and 11, the value collected directly from the CRF will be used, regardless of timing of that visit. If there is no collected value for a given visit per the CRF, the missing value will be replaced from other, non-missing, on-site visits (excluding bridging visits) based on the target analysis windows outlined in Table 3-1. Similar to primary timepoint handling, if there are multiple records equidistant from the target day, the latest of the equidistant records will be utilized.

Table 3-1 Efficacy Windowing for MI Models

Visit	Visit 2	Visit 4	Visit 7	Visit 9	Visit 11
SoA Target Visit Day	22	78	162	218	274
Target Analysis Visit Window	14, 50	51, 120	121, 190	191, 246	247, 304

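### The imputation model leaves out the mandatory on-site Week 48 weight (Visit 13), and its windows run on two clocks, so that weight falls between them when titration lasts 25 days or more

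*SAP*

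**What the plan says.** SAP 3.11.2 says that both imputation methods "will impute based on results from baseline, Visit 2, Visit 4, Visit 7, Visit 9, Visit 11, and the primary timepoint". SAP 3.10.2 gives the same list and describes it thus: "This accounts for planned on-site visits as well as a combined primary timepoint".

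On which visits are on-site, footnote † to Protocol Table 1 says: "The Week 8, 16, 20, 28, 36, 44, and 52 visits may be scheduled in-clinic or as at home telehealth visits". Week 48 is not among them, and the weight row of Table 1 has an unmarked X at Visit 13.

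On clocks, SAP 3.2 says that "study days are numbered relative to the date of randomization which is designated as Day 1". The windows in SAP Table 3-1 are set around the schedule's target days, and the last one (Visit 11, target Day 274) covers Days 247 to 304. SAP 3.11.1 defines the primary timepoint on another clock: the non-missing on-site visit "closest to day 365 within a window of 305 to 425 days from therapeutic dose start date will be selected". SAP 3.10.2 refers to Table 3-1 for the combined primary timepoint, but the table has no such column.

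**The concern.** The limits 304 and 305 look as though one window ends where the next begins. They would do so only if both counted from randomization. Because the second counts from therapeutic dose start, a stretch as long as the titration opens between them, and Visit 13 has no place of its own in the model to catch a weight recorded there.

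For a patient without a weight in the primary window, the model then predicts from Visit 11 (Day 274) although a later on-site weight exists. That runs against the stated purpose of the wide windows in SAP 3.11.2, which is to use as much of the collected data as possible. The same imputed weights feed the two BMI responder key secondaries (SAP 4.3.5), and SAP 3.10.3 carries the method over to the hunger score. At stake is the precision of a few imputed values.

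**Working it through.** **Design figure.** After 20% dropout, 64 versus 32 patients remain. With SD 10 and difference 10, the standard error is 10 × √(1/64 + 1/32) = 2.165. Power at two-sided 0.05 is 99.6% (normal) or 99.55% (noncentral t), which reproduces the stated ~99.5%. The point below does not depend on it.

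**Schedule days.** Trial day = 7 × (week − 1) + 1 gives Visit 11 = 274, Visit 13 = 330, Visit 14 = 358, Visit 15 = 386 and Visit 16 = 414, as in Table 1.

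**Titration length T (days from Day 1 to therapeutic start).** The rule is redacted, so T is assumed.
- Week labels: 56 − 52 = 4 weeks and 60 − 52 = 8 weeks, so T = 28 to 56.
- Schedule days: 386 − 365 = 21 and 414 − 365 = 49, so T = 21 to 49.

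**Position of the primary window.** Days from therapeutic start = trial day − (1 + T). The window 305 to 425 is therefore trial days 306 + T to 426 + T. Table 3-1 ends at 304, so trial days 305 to 305 + T are in neither.

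| T | Uncovered trial days | Visit 13, days from start | Visit 15, days from start |
|---|---|---|---|
| 21 | 305–326 | 308 (in) | 364 (in) |
| 28 | 305–333 | 301 (out) | 357 (in) |
| 49 | 305–354 | 280 (out) | 336 (in) |
| 56 | 305–361 | 273 (out) | 329 (in) |

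**Cut-offs.**
- Visit 13 is in the primary window if 330 − (1 + T) ≥ 305, that is T ≤ 24. It is lost for all 29 values of T from 28 to 56, and for 25 of the 29 values from 21 to 49.
- Held 4 days late, Visit 13 is kept up to T = 28; held 4 days early, only up to T = 20.
- An on-site Visit 14 is kept up to T = 52.
- Visit 15 is kept for every T from 0 to 56.
- Counting the start day as day 1 moves each cut-off by one day.

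**Patients affected.** Assume 24 dropouts (20% of 120) spread evenly over 364 + T days, and count those who leave after Visit 13 and before the next on-site visit inside the primary window.
- T = 28, next visit 14: 24 × 28/392 = 1.7.
- T = 28, next visit 15: 24 × 56/392 = 3.4.
- T = 56, next visit 15: 24 × 56/420 = 3.2.

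If instead every leaver has a prompt on-site early-termination weight, those lost are the weights dated 305 to 305 + T: 24 × 29/392 = 1.8 at T = 28 and 24 × 57/420 = 3.3 at T = 56. The size is the same.

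**Illustration of precision.** If weight followed a random walk, prediction variance from Visit 13 relative to Visit 11 would be (386 − 330)/(386 − 274) = 0.50, or (414 − 330)/(414 − 274) = 0.60. That is a 40–50% reduction for those few patients only, and the random walk is an assumption that the documents do not make.

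**The case against.** A reader might infer that most patients lose their latest weight before end of treatment. The documents do not support that. Visit 15 is an on-site visit with a weight and lies in the primary window for every T considered, so patients whose end of treatment is Visit 16 keep it. At T = 21, which the schedule days suggest for an end of treatment on Day 386, Visit 13 is itself in the window. Nor is the weight discarded everywhere: the LOCF analysis (SAP 4.3.4.3) and the by-visit summaries (SAP 4.3.2) still use it. These limits stand.

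A reader might also count patients still in progress, whom Protocol 7.4 says will be imputed. SAP 3.12.1 bases formal testing on a pivotal cohort of patients who have completed or discontinued, so ongoing patients enter only the supportive all-patients analysis.

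Under wash-out imputation the setmelanotide arm is imputed from baseline alone, so only the placebo step can gain. If a third of the affected dropouts are on placebo, that is 1.7/3 to 3.4/3, or about 0.6 to 1.1 patients.

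The strongest objection concerns the remedy. The retrieved-dropout regression is fitted by arm to off-treatment patients and already has 7 coefficients (intercept and six weights). At 20% dropout the placebo arm of 40 has about 8 dropouts. An eighth coefficient would leave no residual degrees of freedom even if all 8 were retrieved, and failure of that model sends the analysis to wash-out. This stands against adding Visit 13 to that step unconditionally.

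It may also be said that Table 3-1 is only a fallback, since recorded visit values are used whatever their timing. That rule covers the listed visits only and does not rescue Visit 13.

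**Conclusion.** The point holds in limited form. The sentence about planned on-site visits is inaccurate, because Visit 13 is one and is missing. The windows use different clocks, and a Visit 13 weight on its target day is unused in the imputation when T is 25 days or more. How many patients that covers cannot be computed, because the titration rule and the definition of therapeutic start are redacted.

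On even dropout, about 1.7 to 3.4 of 24 dropouts are affected, and fewer where wash-out is used. The consequence is a modest loss of precision in a few imputed values. A reader might infer a threat to power, to type I error or to the primary result; nothing in the documents or the arithmetic shows one.

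**What to change.** - State in SAP 3.11.1 and Table 3-1 which clock each window uses.
- Add a Visit 13 column to Table 3-1: target Day 330, from Day 305 to the day before the patient's own primary window opens.
- Add a precedence rule: a Visit 13 weight selected as the primary value is not also used as a predictor. This is needed when T is 24 days or less.
- Include Visit 13 in the MCMC step and in the placebo MAR step of the wash-out method.
- Include it in the retrieved-dropout regression only if the number of retrieved dropouts per arm supports it, for example by replacing an earlier visit so that the coefficient count does not rise. If it stays out, Visit 13 helps under that method only to fill intermittent gaps, and the SAP should say that this was a choice.
- Correct the sentence in SAP 3.10.2 about planned on-site visits.

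The cost is SAP wording and one more variable in PROC MI, with a slightly higher risk of non-convergence. The weights are already collected.
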